11.3.4 Interim Analyses

No interim analyses are planned for this study.

12 DATA HANDLING AND RECORD KEEPING

12.1 Data Collection

In compliance with GCP, the source data, i.e. medical records/medical notes, etc, should be clearly marked and permit easy identification of a subject's participation in the specified clinical study.

Source data identification and location will be specified in a stand-alone document signed by the investigator(s).

The investigator must record all data relating to protocol procedures, study drug administration, laboratory data, safety, pharmacodynamic/efficacy data on the source documents and report requested data on electronic eCRFs provided for the study (see Section 12.2).

To ensure accurate, complete, and reliable data, the sponsor or its representative will provide instructional material to the study site(s), as appropriate. Training session will be given during a start-up/initiation meeting for instructions on the completion/data entry of any source data documents and eCRF.

The investigators or their designees must verify that all data entries in the eCRF are accurate and consistent with source data records. If certain information is not available for a particular timepoint and/or subject, specific instructions should be followed, e.g. to document that the procedure was either not done or not applicable.

12.2 Data Reporting

Electronic data capture will be utilised for collecting subject data. The study site is required to have a computer and internet connection available for study site entry of clinical data. All entries in the eCRF will be made under the electronic signature of the person performing the action. This electronic signature consists of an individual and confidential username and password combination. It is declared to be the legally binding equivalent of the handwritten signature. Only sponsor authorised users will have access to the eCRF as appropriate to their study responsibilities. Users must have successfully undergone software application training prior to entering data into the eCRF.

12.3 Data Management

Details of all data management procedures, from the initial planning to the archiving of final datasets/documents following database freeze/lock will be documented in appropriate stand-alone data management and validation plan(s).

Data management will be conducted by a contract research organisation (CRO) approved by the sponsor. All data management procedures will be completed in accordance with the sponsor and contracted CRO standard operating procedures (SOPs). Prior to data becoming available for processing at the assigned data management CRO, they will be monitored. Data documentation removed from the CRU will be tracked by the CRO and the monitor.

The sponsor will ensure that an appropriate eCRF is developed to capture the data accurately and that suitable queries are raised to resolve any missing or inconsistent data. At the end of the study, the investigator will receive the data from the clinical study in an electronic format (PDF files), which will be an exact copy of the eCRF, and will include the full audit trail, for archiving purposes and future reference.

Any queries generated during the data management process will also be tracked by the contracted data management CRO. It is the central study monitor's responsibility to ensure that all queries are resolved by the relevant parties.

The CRO will also ensure, via SAE reconciliation, that SAE data collected in the eCRF are consistent with SAE data held in the sponsor's GPS department (and vice versa).

The coding of an AE, medical history, surgical procedures and concomitant medication terms will be performed by a contracted CRO, managed by the sponsor's Biometry department, and reviewed and approved by the sponsor. Concomitant medications will be coded using WHODRUG-B3 and AEs/medical history terms will be coded using MedDRA.

Only data from enrolled subjects will be reported in the eCRFs and collected in the sponsor's database.

For screen failure subjects, at least the Unique Subject Identifier, the date of informed consent signature, the reason for screen failure and the potential AEs will be reported in the eCRFs and collected in the sponsor's database.

For run-in failure subjects, at least all data recorded for screen failure subjects will be collected in addition to NRS data and previous/concomitant medications.

12.4 Record Keeping

The investigator will keep records of all original source data. This might include laboratory tests, medical records, and clinical notes.

During the prestudy and initiation visits, the monitor must ensure the archiving facilities are adequate and archiving/retention responsibilities of the investigator have been discussed.

Study documents should be retained until at least two years after the last approval of a marketing application in an ICH region and until there are no pending or planned marketing applications in an ICH region (that is at least 15 years) or at least two years have elapsed since the formal discontinuation of clinical development of the product. However, these documents should be retained for a longer period if required by applicable regulatory requirements or by an agreement with the sponsor. The investigator should take measures to prevent accidental or premature destruction of these documents. The final archiving arrangements will be confirmed by the monitor when closing out the study site. The sponsor will inform the investigator, in writing, as to when these documents no longer need to be retained.

If the principal investigator relocates or retires, or otherwise withdraws responsibility for maintenance and retention of study documents, the sponsor must be notified (preferably in writing) so that adequate provision can be made for their future maintenance and retention.

13 REGULATORY AND ETHICAL CONSIDERATIONS

13.1 Regulatory Considerations

The study will be conducted in compliance with IECs/IRBs, informed consent regulations, the Declaration of Helsinki and ICH Guidelines related to GCP. Any episode of noncompliance will be documented. The electronic data capture (EDC) system will comply with the FDA, 21 CFR Part 11, Electronic Records, Electronic Signatures, and FDA, Guidance for Industry: Computerized Systems Used in Clinical Trials.

In addition, the study will adhere to all applicable international and local regulatory requirements.

All or some of the obligations of the sponsor will be assigned to a CRU or a CRO.

An identification code assigned to each subject will be used in lieu of the subject's name to protect the subject's identity when reporting AEs and/or other trial-related data (see Section 3.4.1).

13.2 Ethical Review Considerations

The following documents should be submitted to the relevant ethics committee(s) (EC) for review and approval to conduct the study (this list may not be exhaustive):

- Protocol/amendment(s) approved by the sponsor,
- Currently applicable IB or package labelling,
- Relevant investigator's curriculum vitae,
- Subject information and informed consent document(s) and form(s),
- Subject emergency study contact cards,
- Recruitment procedures/materials (advertisements), if any.

The EC(s) will review all submission documents as required, and a written favourable opinion for the conduct of the study should be made available to the investigator before initiating the study. This document must be dated and clearly identify the version number(s) and date(s) of the documents submitted/reviewed and should include a statement from the EC that they comply with GCP requirements.

The study may begin at the investigative site(s) only after receiving this dated and signed documentation of the EC approval or favourable opinion.

During the study, any update to the following documents will be sent to the EC either for information, or for review and approval, depending on how substantial the modifications are: (1) IB; (2) reports of SAEs; (3) all protocol amendments and revised informed consent(s), if any.

At the end of the study, the EC will be notified about the study completion.

13.3 Subject Information Sheet and Consent

The investigator is responsible for ensuring that the subject understands the potential risks and benefits of participating in the study, including answering, orally and/or in writing, to any questions the subject may have throughout the study and sharing any new information that may be relevant to the subject's willingness to continue his or her participation in the study in a timely manner.

The subject information sheet and consent document will be used to explain the potential risks and benefits of study participation to the subject in simple terms before the subject is entered

into the study, and to document that the subject is satisfied with his/her understanding of the study and desires to participate.

The investigator is ultimately responsible for ensuring that the EC-approved informed consent is appropriately signed and dated by each subject prior to the performance of any study procedures. Informed consent obtained under special circumstances may occur only if allowed by local laws and regulations.

13.4 Final Report Signature

The investigator or designee will be proposed to review and sign the clinical study report for this study, indicating agreement with the analyses, results, and conclusion of the report.

14 INSURANCE AND FINANCE**14.1 Insurance**

The sponsor declares that it has taken out a product liability insurance covering all subjects screened and enrolled in this study in respect to risks involved in the study.

14.2 Financial Agreement

Since this study is to be performed in partnership with a CRO, separate financial agreements between the sponsor and the CRO on one side, and the CRO and the CRU on the other side, will be signed prior to initiating the study, outlining overall sponsor and investigators responsibilities in relation to the study.

15 **QUALITY CONTROL AND QUALITY ASSURANCE**

To ensure accurate, complete, and reliable data, the sponsor or its representatives will provide instructional material to the study sites, as appropriate. A start-up training session will be done prior to screening start to instruct the investigators and study coordinators. This session will give instruction on the protocol, the completion of the eCRF, and all study procedures.

15.1 Protocol Amendments and Protocol Deviations and Exceptions

15.1.1 Protocol Amendments

In the event that an amendment to this protocol is required, it will be classified into one of the following three categories:

- Non-substantial amendments are those that are not considered ‘substantial’ (e.g. administrative changes) and as such only need to be notified to the IECs or regulatory authorities for information purposes.
- Substantial amendments are those considered ‘substantial’ to the conduct of the clinical study where they are likely to have a significant impact on:
 - the safety or physical or mental integrity of the subjects,
 - the scientific value of the study,
 - the conduct or management of the study,
 - or the quality or safety of the study drug used in the study.

Substantial amendments must be submitted to and approved by the IECs and relevant regulatory authorities, according to local regulations, prior to implementing changes.

- Urgent amendments are those that require urgent safety measures to protect the study subjects from immediate hazard and as such may be implemented immediately by the sponsor with subsequent IECs and regulatory authority notification, forthwith.

The principal investigator and the sponsor will sign the protocol amendment.

15.1.2 Protocol Deviations and Exceptions

Protocol deviations are defined and classified as either major or minor for a given study. Major deviations (or a combination of minor becoming major) may or may not impact on the analysis population. All minor and major protocol deviations will be identified and recorded by CRU personnel and should be traceable.

Major Protocol Deviation Definition

Any changes in the study design, study conduct and/or procedures that are not in accordance with the protocol and any study materials originally approved by the IEC and which may affect the subject’s rights, safety or well-being, or the completeness, accuracy and reliability of the study data.

Minor Protocol Deviation Definition

Any changes in the study design, study conduct and/or procedures that are not in accordance with the protocol and any study materials originally approved by the IEC but that do not have an important impact on the subject’s rights, safety or well-being, or the completeness, accuracy and reliability of the study data.

As a matter of policy, the sponsor will not grant exceptions to protocol-specific entry criteria to allow subjects to enter a study. If under extraordinary circumstances such action is considered ethically, medically, and scientifically justified for a particular subject, prior approval from the sponsor is required before the subject will be allowed to enter the study.

If investigative CRU personnel learn that a subject who did not meet the protocol eligibility criteria was entered in a study (eligibility criteria deviation), they must immediately inform the sponsor. Such subjects will be discontinued from the study, except in exceptional circumstances, following review and written approval by the sponsor.

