Audit	Systematic and independent examination of the study-related activities and documents to determine whether the evaluated study-related activities were conducted, and the data were recorded, analysed, and accurately reported according to the protocol, sponsor's standard operating procedures, good clinical practices, and the applicable regulatory requirement(s).
Compliance	Adherence to all the study-related requirements, good clinical practices requirements and the applicable regulatory requirements.
Double-blinding	Procedure to which usually the subject(s), investigator(s), monitor(s), and in some cases, selected sponsor personnel, are being unaware of the treatment assignment(s).
End of Study	Date of the last visit or last scheduled procedure shown in the study schedule for the last active subject in the study.
Enrol / Randomise	Act of assigning a subject to a treatment. Subjects who are enrolled in the study are those who have been assigned to a treatment.
Enter / Consent	Act of obtaining informed consent for participation in a clinical study from subjects deemed- or potentially eligible to participate in the clinical study. Subjects entered into a study are those who sign the informed consent document directly.
Ethics Committee	Board or committee (institutional, regional, or national) composed of medical professional and non-medical members whose responsibility is to verify that the safety, welfare, and human rights of the subjects participating in a clinical study are protected.
Investigator	Physician responsible for the conduct of a clinical study at a study site. If a study is conducted by a team of individuals at a study site, the investigator is the responsible leader of the team and may be called the principal investigator.
Run-in	Extension of the screening period to select subjects who have potential to respond to Dysport.
Screen	Act of determining if an individual meets minimum requirements to become part of a pool of potential candidates for participation in a clinical study. In this study, screening involves invasive procedures (for example, blood draws). For this type of screening, informed consent for these screening procedures and/or tests shall be obtained.
Subject	Individual who is or becomes a participant in clinical research, either as a recipient of the test article or as a control.
ABBREVIATION	Wording Definition
ACE	Angiotensin converting enzyme
AE	Adverse event
AESI	Adverse event of special interest

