3 INVESTIGATIONAL PLAN

3.1 Overall Study Design and Plan

The study will consist of two sequential parts, the first being to identify subjects who will potentially benefit from intradermal Dysport injection, 'responders', who will then progress to the second part, which is the double-blind study of the intradermal injection of Dysport or placebo:

- Part A: A double-blind, randomised, initial two-period cross-over run-in part, extended screening period of placebo or local anaesthetic (lidocaine),
- Part B: A single-dose, double-blind, randomised, parallel part with one of the three different doses of Dysport or placebo.

To ensure subjects will potentially benefit from intradermal injection of Dysport, they will be tested for responsiveness to local anaesthetic (lidocaine).

In Part A, and upon consent and successful screening of medical eligibility, subjects will be injected (injection test 1) during a pre-randomisation run-in period in a double blind fashion with either saline or local anaesthetic (lidocaine) and assessed for pain perception up to 24 hours post-injection. One week later, they will be crossed over, injected with the other agent (injection test 2) and assessed for pain perception up to 24 hours post-injection. Pain intensity will be scored using a 11-point NRS (from score 0 for "no pain" up to 10 for "worst possible pain").

If subjects are assessed as responders, they will enter in Part B, and will be trained and provided with an Actiwatch® to enable them to record twice a day their spontaneous NRS scores.

[figure not shown]
Before dosing on Day 1, the subjects will perform baseline assessments including a quantitative sensory testing (QST) assessing allodynia, hyperalgesia and conditioned pain modulation, completion of a QoL questionnaire, and safety assessments (physical examination, vital signs measurements, collection of adverse events (AEs) and recording of concomitant medication).

Subjects will be dosed if considered as consistent in pain perception from the screening visit (i.e. variability < 2 for the average spontaneous NRS score pre-injection tests in Part A, pre-QST and pre-dosing and as clinically plausible per investigator's judgement).

Subjects will then be assessed for pharmacodynamics and safety for a total of 16 weeks post-dose.

Subjects will be discharged from the study after safety assessments (physical examination, vital signs) during an end of study (EoS) visit.

The study design is presented in [Figure 2](#).

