3.3 Study Duration

This study will consist of:

- A screening visit: 28 days maximum before IMP dosing,
- A Part A, pre-randomisation run-in period:
 - First injection test: 21 days maximum before IMP dosing,

- Second injection test: one week after first injection test, 14 days maximum before IMP dosing,
- A Part B, randomised double-blind period:
 - A baseline period including a QST and Actiwatch® training, safety assessments and a QoL: within 7 days before IMP dosing,
 - A one-day IMP dosing,
 - A 16-week randomised double-blind period.

Subjects are expected to participate in this study for a maximum of 20 weeks.

The study will be considered to have started when the first subject has provided signed informed consent and will be considered to have ended after the last subject has completed his EoS visit.

The overall study is anticipated to last approximately one year.

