3.5 Stopping Rules and Discontinuation Criteria

The complete study can be terminated prematurely at any time if the sponsor judges it necessary for any reason. In that case, all scheduled procedures and assessment for subjects who are still in the study will be performed.

Some possible reasons for the closure of a study site may include:

- Failure of the investigator staff to comply with the protocol or with the GCP guidelines,
- New and significant safety concerns,
- Inadequate subject's recruitment.

During the conduct of the study, all AEs including serious AEs (SAEs) will be reviewed as they are reported from the study site to identify new and significant safety concerns.

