4.4 Withdrawal of Subjects

In accordance with the declaration of Helsinki and International Council for Harmonisation (ICH) GCP, each subject is free to withdraw from the study at any time, for any reason (e.g. withdrawal of consent, AE).

The investigator can withdraw a subject from the study at any time for any reason (e.g. protocol deviation, non compliance with the protocol conditions, lack of cooperation, in the event of concurrent illness, AE, or other reasons concerning the health or well-being of the subject).

The reason for and date of withdrawal from the study must be recorded in the eCRF.

If withdrawal is based on subject's decision every attempt will be made to determine:

- The reason for withdrawal,
- Whether the subject also decides to withdraw his/her consent for the sponsor to collect and use the data collected up to the withdrawal point.

Data collected prior to subject withdrawal may be kept in study records and shared for further analyses unless the subject formally specifies his/her decision to withdraw consent for using data already collected.

Should a subject be withdrawn from the study after IMP dosing and before normal study completion, all efforts will be made to complete the EoS assessments and report the observations up to the time of withdrawal as thoroughly as possible. A complete final evaluation at the time of the subject's withdrawal should be made whenever possible.

Subjects who withdraw within the first six weeks after IMP dosing for reasons other than lack of efficacy will be replaced. Replacement subjects will receive the same schedule and treatment as the subject they have replaced.

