7.1.6 Adverse Events of Special Interest

The effects of Dysport and all BTX products may spread from the area of injection to produce symptoms consistent with BTX effects. These symptoms have been reported hours to weeks after injection. Remote spread of toxin that affects swallowing and breathing can be life threatening, and there have been reports of death. The risk of symptoms is increased in subjects who have underlying conditions (e.g. disorders of the neuromuscular junction) that would predispose them to these symptoms. Dysport is contraindicated in individuals with known hypersensitivity to any BTX preparation or to any of the components in the formulation. Adverse events of special interest (AESIs) for Dysport are AEs that suggest a possible remote spread of effect of the toxin or hypersensitivity. A list of preferred terms of AESIs will be provided in the statistical analysis plan (SAP). All AEs will be monitored by the sponsor to determine if they meet the criteria of AESIs. These AESIs will be further analysed to determine if there is a plausible possibility that they represent distant spread of toxin or hypersensitivity. In order to perform the analysis, variables including alternate aetiology (medical history, concomitant medication, or diagnosis which could account for the symptoms), location of Dysport administration, and temporal relationship to Dysport administration will be considered by the sponsor.

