5.7.1.2 Statistical/analytical issues

Adjustments for Covariates

Not applicable

Handling of Dropouts or Missing Data

The strategy for missing data handling is specified in each relevant section.

Interim Analyses and Data Monitoring

Please refer to section 3.

Multicentre Studies

Not applicable

Multiple Comparisons/Multiplicity

No formal statistical significance testing will be performed.

Use of an "Efficacy Subset" of Subjects

Not applicable

Active-Control Studies Intended to Show Equivalence (if applicable)

Not applicable

Examination of Subgroups

Subgroups analyses will be detailed in the concerned sections.

5.7.2 *Pre-randomisation run-in period*

A listing presenting NRS data will be provided. The listing will present, by subject, the planned visit and timepoint, the treatment administered, the assessment dates and the NRS scores.

5.7.3 *Randomised double-blind period: Analysis of Primary Efficacy Endpoint*

5.7.3.1 *Endpoint, Treatment Effect and Estimand Definition*

To assess the primary objective, the treatment policy estimand is defined by the following key attributes:

- Population: Subjects in the randomized population
- Assessment: Worst pain and average pain within the last 12 hours as assessed by the spontaneous NRS score
- Variables (Endpoints): Described in table below
- Population-level summary (estimate of the treatment effect): Described in table below

Variables (Endpoints)	Population-level summary (estimate of the treatment effect)
Time to onset i.e. time to decrease from baseline of two points in the spontaneous NRS score. Derivation: First scheduled time point for which the change from baseline is ≤ -2 points.	The number (%) of subjects who reach the time to onset in each treatment group. The mean time to onset in each treatment group
Peak effect i.e. maximal decrease from baseline in the spontaneous NRS score. Derivation: Minimum change from baseline amongst the scheduled timepoints	The mean peak in each treatment group
Time to peak-effect i.e. time to reach the peak-effect Derivation: First timepoint for which the peak effect is reached	The mean time to reach the peak-effect in each treatment group

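### Discontinuing dosed subjects found ineligible ends only their scheduled data collection and leaves truncated records in the all-randomised analysis

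*Protocol*

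**What the plan says.** Protocol 15.1.2 sets the default for a subject found after entry not to have met the eligibility criteria: "Such subjects will be discontinued from the study, except in exceptional circumstances, following review and written approval by the sponsor". Discontinuation is from the study, not from treatment. The protocol's definitions make entry the act of consenting ("Subjects entered into a study are those who sign the informed consent document directly"), so the rule covers dosed and undosed subjects alike.

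Protocol 3.1 describes Part B as "A single-dose, double-blind, randomised, parallel part with one of the three different doses of Dysport or placebo", and Protocol 3.3 follows dosing with "A 16-week randomised double-blind period".

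For the primary endpoints, SAP 5.7.3.1 sets "Population: Subjects in the randomized population" under a treatment-policy strategy. SAP 5.7.3.2 does no missing-data handling in the primary analysis. SAP 2.6 drops the protocol's planned sensitivity analyses for rescue medication and missing data, subject to confirmation at the blind data review.

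Protocol 4.4 names protocol deviation among the reasons for which the investigator may withdraw a subject, and adds: "Subjects who withdraw within the first six weeks after IMP dosing for reasons other than lack of efficacy will be replaced".

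**The concern.** After the Day 1 injections the exposure has happened and cannot be withdrawn. Applied to a dosed subject, the rule in 15.1.2 protects nobody from further treatment. It stops observation of someone who still counts in the analysis.

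Two things are at stake.

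- **Efficacy.** The four primary endpoints are read off the whole 16-week course of pain scores, so an early cut-off changes their values. No planned analysis corrects for this.
- **Safety.** On symptoms of toxin spread, Protocol 7.1.6 says: "These symptoms have been reported hours to weeks after injection". It adds that risk is higher with certain underlying conditions, such as disorders of the neuromuscular junction. Exclusion criteria 4 and 7 screen out conditions and agents that interfere with neuromuscular function or transmission. A dosed subject later found to breach one of these may be among those for whom continued scheduled contact is most informative.

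**Working it through.** **The plan's own figure.** Allocation is 3:1:3:1:3:1 in blocks of 12 (Protocol 3.4.1.2), with about 24 subjects (11.2). 24 / 12 = 2 blocks, giving 6 per Dysport dose and 3 x 2 = 6 pooled placebo. The stated six per arm is reproduced. There is no power calculation, and this point does not depend on one.

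**What ends and what remains for a dosed subject.**

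- *Ends:* twice-daily NRS entries; the QST and SF-36 assessments not yet reached; the scheduled calls; the Week 6 scar examination if not yet reached; active collection of new AEs regardless of relatedness. The AE definition (Protocol 7.1.1) and the treatment-emergent window (SAP 5.8.3) both close at EoS/ED.
- *Remains:* an exit evaluation where possible (4.4); follow-up of ongoing AEs, up to 30 days after the end of the study (7.1.2.2); reporting of related AEs that the investigator learns of later (7.1.2.3); follow-up of persisting examination abnormalities (7.2.1).

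The EoS/ED column of the schedule (18.1) has no QST or SF-36. Exit before Week 6 therefore loses both post-dose assessments, and exit between Weeks 6 and 12 loses one.

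**Entries lost.** Planned entries = 16 weeks x 7 days x 2 = 224. Entries lost on exit at Week D = (16 - D) x 7 x 2.

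| Exit at week | Days lost | Entries lost | Share of follow-up |
|---|---|---|---|
| 2 | 98 | 196 | 87.5% |
| 4 | 84 | 168 | 75% |
| 6 | 70 | 140 | 62.5% |
| 8 | 56 | 112 | 50% |
| 12 | 28 | 56 | 25% |

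Each entry collects an average and a worst score (9.1.3). The number of scores is therefore double, and the percentages do not change.

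**Weight in the arm.** One subject is 1/6 = 16.7% of an arm. If exit falls in the replacement window, seven are randomised to that arm and the share is 1/7 = 14.3%. Replacement restores the number followed, but the truncated subject remains in the randomised population.

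**Effect on the endpoints (SAP 5.7.3.1).**

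- Duration is the last timepoint with a change of -2 or lower, minus time to onset. Once onset has been seen, cutting the record can only shorten that subject's duration or leave it unchanged.
- Peak is the minimum change among scheduled timepoints. Fewer timepoints can reduce the peak but cannot increase it.
- A subject who exits before onset counts as not reaching it and drops out of the mean duration.

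**Illustration on assumed values.** Suppose all six subjects reach onset at Week 2 with effect lasting to Week 16, so true duration is (16 - 2) x 7 = 98 days. One subject exits at Week D, with observed duration (D - 2) x 7. The arm mean falls by (98 - observed) / 6.

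- Week 4: (98 - 14) / 6 = 14.0 days
- Week 6: (98 - 28) / 6 = 11.7 days
- Week 8: (98 - 42) / 6 = 9.3 days
- Week 12: (98 - 70) / 6 = 4.7 days

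If the Week 4 case is replaced by a subject with the full 98 days, the fall is 84 / 7 = 12.0 days.

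**The case against.** The strongest case is that this is generic policy wording that would rarely reach a dosed subject. Entry means consent, so much of its scope is undosed subjects. Eligibility is checked at screening, at baseline and again before dosing on Day 1. The sponsor may approve exceptions in writing, which could include a dosed subject. The study is descriptive and has no tests to distort. All of this stands and limits how often the problem would arise. It does not change what the default does when it applies: retention needs case-by-case approval in exceptional circumstances. Monitoring against source documents continues through the study (15.2), so late discovery is foreseeable.

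A reader might infer more than the documents support.

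- *That safety follow-up is lost.* It is shortened. The exit evaluation and the later provisions listed in the working remain, so a delayed event judged related still has a reporting route once the investigator hears of it.
- *That 15.1.2 contradicts the estimand.* The intercurrent events listed in Protocol 11.3.3.2 concern rescue medication only. Study discontinuation is formally missing data, and nothing planned handles it.
- *That the primary endpoints become missing.* They can often still be derived from the observed scores, but from a truncated record. The SAP's listing of subjects with missing values would describe such cases at most. It would not correct them.
- *That Protocol 3.5 already keeps dosed subjects under observation if the sponsor stops the study.* Its words are "all scheduled procedures and assessment for subjects who are still in the study will be performed". It does not mention dosing and does not cover someone already discontinued, so it is not inconsistent with 15.1.2.

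**Conclusion.** The point holds for subjects already dosed. The default in 15.1.2 cannot alter their exposure. It cuts short scheduled data collection and active AE collection, and it leaves a truncated record in the all-randomised analysis. The primary analysis has no remedy for this, and the missing-data sensitivity analyses are dropped subject to blind review.

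Per case, the loss runs from 87.5% of the twice-daily entries for exit at Week 2 to 25% at Week 12, in a subject who is about 1/6 of an arm, or 1/7 if replaced. These shares follow from the schedule and arm size. The shifts in mean duration rest on assumed onset and duration and only illustrate scale. The documents give no frequency, so the expected impact across the study cannot be stated. The point is still worth correcting, because with six per arm one case matters and the assessments that would be kept are already scheduled.

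**What to change.** Reconcile Protocol 15.1.2 with 4.4 and 11.3.3.2 and with SAP 5.7.3, so that:

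- for a subject already dosed, an eligibility deviation alone does not end scheduled data collection to Week 16;
- consent withdrawal and the investigator's safety judgement are left as they are;
- the deviation is recorded as major, the subject stays in the randomised and safety populations, and the deviation is dealt with through the per-protocol population.

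SAP 5.7.3.3 repeats the analysis on the per-protocol population only if at least two patients in the same treatment group differ between the populations. A lone case would therefore appear in the listing of violated criteria (SAP 5.2) without triggering that analysis, and the SAP should say so.

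Nothing here proposes a rule on whether to dose a subject found ineligible beforehand.

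The cost is a short protocol amendment with no new procedures. Because it changes follow-up of exposed subjects, it may count as substantial under 15.1.1 and so need ethics and regulatory approval.
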